13.2 Medical History

Medical history will be coded using the latest available version of Medical Dictionary for Regulatory Activities (MedDRA). Medical history will be summarized as the numbers and percentages of subjects by MedDRA PT as event category and MedDRA SOC as summary category, and sorted by SOC and PT in alphabetical order. Each subject will be counted only once within each PT or SOC.

Listing of medical history data by subject will include coded terms and all the relevant data fields as collected on the Medical History eCRF page.

13.3 Disease History

Disease histories are collected on NSCL Cancer Diagnosis, Colorectal Cancer Diagnosis, Gastric and GEJ Cancer, Castrate-Resistant Prostate Cancer, Melanoma Diagnosis, Ovarian Cancer, Metastatic Breast Cancer, Adrenocortical Carcinoma Diagnosis, Mesothelioma Cancer Diagnosis, Renal Cell Carcinoma Diagnosis, Head and Neck Cancer Diagnosis, and Urothelial Carcinoma Diagnosis eCRF pages. Partial date will be imputed as described in the Section 18.1.

The disease history table will include descriptive statistics for the following variables:

- Sub-site of tumor

Summary of tumor sub-sites applies to NSCLC, MBC, Gastric and GEJ cancer, CRC, ovarian cancer, melanoma cancer, ACC, mesothelioma, urothelial carcinoma, HNSCC where pre-defined sub-sites or standard terms will be captured on the eCRF pages.

- Time since first diagnosis (years), defined as (the first dosing date – the date of first diagnosis)/365.25

- Time since metastatic or locally advanced disease (months), defined as (the first dosing date – the date of first occurrence of metastatic or locally advanced disease)/30.4375
- Time since last disease progression (months), defined as (the first dosing date - the date of last progression of disease)/30.4375
- Tumor Node Metastasis Classification of Malignant Tumors (TNM) at initial diagnosis
- TNM at study entry

Listing of disease history will be provided with all relevant data (tumor sub-site, initial diagnosis date, first occurrence of metastatic or locally advanced disease, date of last disease progression, TNM classification) and derived variables used in the above table.

Eligibility for platinum-based therapy is collected on Platinum Ineligibility eCRF page for urothelial carcinoma and HNSCC cohorts. It will be summarized for the following categories:

- Eligibility for platinum-based therapy
 - Yes
 - No
 - Impaired renal function
 - Hearing loss (25 decibels at 2 contiguous frequencies)
 - Peripheral neuropathy
 - Other

Listing of eligibility for platinum-based therapy will be provided with all relevant data (eligibility, reason for ineligibility, and date ineligibility defined).

13.4 PD-L1 Expression Status and Biomarker

PD-L1 expression status will be collected using Pathology Report Form. The percentages of viable tumor cells that exhibit PD-L1 membrane staining at any intensity are evaluated. No staining should be scored as “0”, weak staining as “1+”, moderate staining as “2+”, and strong staining as “3+”.

PD-L1 expression status will be classified as positive or negative based on the following cut-offs:

- For tumor cells:
 - Subjects will be considered PD-L1 expression positive (negative) if at least (less than) 5% of the tumor cells show PD-L1 membrane staining $\geq 1+$, respectively. This will be used as the primary cut-off.
 - Subjects will be considered PD-L1 expression positive (negative) if at least (less than) 25% of the tumor cells show PD-L1 membrane staining $\geq 2+$, respectively. This will be considered as secondary cut-off.

- Subject will be considered PD-L1 expression positive (negative) if at least (less than) 1% of the tumor cells show PD-L1 membrane staining $\geq 1+$, respectively. This will be used as the tertiary cut-off.
- Subject will be considered PD-L1 expression positive (negative) if at least (less than) 50% of the tumor cells show PD-L1 membrane staining $\geq 1+$, respectively. This will be used as the ‘50% cut-off’.
- Subject will be considered PD-L1 expression positive (negative) if at least (less than) 80% of the tumor cells show PD-L1 membrane staining $\geq 1+$, respectively. This will be used as the ‘80% cut-off’.
- For Immune cells:

Subjects will be considered PD-L1 expression positive with regard to immune cell expression if tumor has ‘PD-L1 hotspots’ with at least 10% PD-L1 expressing immune cells. Subjects with an evaluable specimen not meeting this criterion are considered PD-L1 expression negative with regard to immune cell expression. The PD-L1 expression negative subjects will contain subjects from the following categories:

- Negative 1: if there are no tumor associated immune cells (TAICs) present in the specimen.
- Negative 2: if there are TAICs present but no ‘PD-L1 hotspots’.
- Negative 3: if tumor has ‘PD-L1 hotspots’ with $< 1\%$ PD-L1 expressing immune cells.
- Negative 4: if tumor has ‘PD-L1 hotspots’ with 1-9% PD-L1 expressing immune cells.

PD-L1 expression status will be summarized using the following variables:

- PD-L1 expression status based on tertiary cut-off for tumor cells (positive/ negative/ not evaluable)
- PD-L1 expression status based on primary cut-off for tumor cells (positive/ negative/ not evaluable)
- PD-L1 expression status based on secondary cut-off for tumor cells (positive/ negative 1, negative 2 / not evaluable)
 - Negative 1: subjects with $< 5\%$ tumor cells with staining $\geq 1+$
 - Negative 2: subjects with $\geq 5\%$ tumor cells with staining $\geq 1+$, but $< 25\%$ tumor cells with staining $\geq 2+$
 - Negative: combined subjects from Negative 1 and Negative 2 as mentioned above
- PD-L1 expression status based on ‘50% cut-off’ for tumor cells (positive/ negative/ not evaluable)
- PD-L1 expression status based on ‘80% cut-off’ for tumor cells (positive/ negative/ not evaluable)
- PD-L1 expression status based on immune cells (positive/ negative1, negative 2, negative 3, negative 4 / not evaluable if data is collected, or positive/ negative/ not present)

- % of tumor cells with any staining (grade $\geq 1+$) as continuous variable
- % of tumor cells with at least 2+ staining as continuous variable

The percentage of tumor cells with any staining (grade $\geq 1+$) stratified by PD-L1 expression status based on immune cells will be displayed graphically using a boxplot. The association between PD-L1 expression and NSCLC histology (adenocarcinoma, squamous cell carcinoma, others) will be summarized using frequency and percentage in a table.

For the gastric and GEJ cancer cohorts, PD-L1 expression is in addition scored with alternative scoring methodologies, where three scoring methods to evaluate PD-L1 expression status will be used as follows:

- Conventional tumor cell (TC) (cell number-based percentage) scoring method
- Immune cell (IC) rescoring method
- Aggregated (TC + IC) scoring method

Aggregate PD-L1 expression score combines TC and IC scores, and the results will be categorized as follows:

- $< 1\%$ for both TC and IC vs $\geq 1\%$ for either TC or IC
- $< 5\%$ for both TC and IC vs $\geq 5\%$ for either TC or IC
- $< 25\%$ for both TC and IC vs $\geq 25\%$ for either TC or IC

Additional details of these scoring algorithms are specified in the Pathology Report Form (PRF).

PD-L1 expression status (positive vs. negative) at baseline with different cutoff values will be summarized in total for each scoring method. PD-L1 assay status of percentage of PD-L1 positive tumor cells will be summarized as below:

- $< 1\%$
- $\geq 1\%$ to $< 5\%$ (cut-off is 1%)
- $\geq 5\%$ to $< 25\%$, (cut-off is 5%)
- $\geq 25\%$ (cut-off is 25%)

The dates of sample collection for PD-L1 expression analysis will be summarized using the following variables. All subjects with valid PD-L1 expression results will be included for the analysis.

- Time from sampling date to first dose date (months), defined as (the first dosing date – the date of tissue sampling)/30.4375
- Timing related to the first date of prior anti-cancer therapy for metastatic or locally advanced disease (before/ after). If the sampling date is prior to the first date of prior anti-cancer therapy for metastatic or locally advanced disease, it is considered as ‘before’; otherwise, it is considered as ‘after’.

CCI

CCI

CCI

14 Prior and Concomitant Medications/Procedures

Prior and concomitant anti-cancer therapy/ other medications will be coded using the latest available version of WHO Drug Dictionary, and summarized based on SAF.

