Subjects who do not complete 4 weeks of treatment for reasons other than treatment-related AE will be replaced. Subjects in this cohort will be enrolled in selected sites in the USA only.

In 10 mg/kg once weekly cohort the SMC will evaluate overall safety data when all 6 evaluable subjects have completed a minimum 4-week treatment period, and after 12 weeks of observation have been completed for all subjects enrolled in this cohort (see Section 2.2.1).

Expansion cohorts

After an avelumab dose and regimen for further investigation are established, enrollment in expansion cohorts will be opened in up selected tumor indications to determine the safety and clinical activity of avelumab. Subjects will be divided into:

- 4 primary cohorts (N=150 subjects each) of:
 1. NSCLC, post platinum doublet;
 2. NSCLC, first line, does not carry an epidermal growth factor receptor (EGFR) activating mutation or anaplastic lymphoma kinase (ALK) re-arrangements (non-squamous cell histologies require testing if status is unknown);
 3. Gastric and GEJ junction cancer; and

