- Highly** effective contraception (that is, methods with a failure rate of less than 1% per year) for both male and female subjects if the risk of conception exists (Note: The effects of the study treatment on the developing human fetus are unknown; thus, women of childbearing potential and men must agree to use highly effective contraception, defined in [Appendix III](#) or as stipulated in national or local guidelines. **Highly** effective contraception must be used 28 days prior to first study treatment administration, for the duration of study treatment, and at least for 60 days after stopping study treatment. Should a woman become pregnant or suspect she is pregnant while she or her partner is participating in this study, the treating physician should be informed immediately.)

Inclusion criteria for expansion phase:

- Signed written informed consent.
- Male or female subjects aged ≥ 18 years.
- Subjects must have relapsed, refractory, or progressive disease following last line of treatment (with the exception of the NSCLC first-line and gastric and GEJ cancer primary cohorts, which do not require progression). Availability of tumor archival material or fresh biopsies (excluding bone biopsies) is mandatory for eligibility in the expansion cohorts. For subjects in the MBC cohort, the biopsy or surgical specimen must have been collected within 90 days prior to the first IMP administration. Specifically, the following will be required:

Primary expansion cohorts

- NSCLC post platinum doublet:** Histologically or cytologically confirmed stage IIIB or stage IV NSCLC that has progressed after 1 line of platinum-containing doublet chemotherapy. Subjects should have received only 1 line of platinum-containing treatment for metastatic disease (i.e., adjuvant treatment with a platinum-containing regimen is not sufficient for eligibility because not received in the context of a metastatic disease). Subjects in the NSCLC cohort will only be enrolled in the USA.
- NSCLC first line:** Stage IV (per 7th International Association for the Study of Lung Cancer [IASLC] classification) or recurrent NSCLC that is histologically proven. Subjects must not have received treatment for their metastatic or recurrent disease. No activating EGFR mutation nor ALK translocation / re-arrangement (non-squamous cell histologies require testing if status is unknown).

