The association between unconfirmed/confirmed objective response and PD-L1 status (based on tertiary cut-off) will be stratified by PD-L1 sampling time related to the first date of prior anti-cancer therapy for metastatic or locally advanced disease (before, after) and summarized in a table. This will apply to post-platinum doublet NSCLC cohort.

[figure not shown]
The maximum target lesion percentage reduction vs. percentage of tumor cells with any staining ($\geq 1+$) or with $\geq 2+$ staining will be displayed graphically using scatterplot.

Subgroup information and BOR, PFS, or OS will be presented in three separate data listings.

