- If the day is missing, it will be imputed to the 15th day of the month; if both day and month are missing and the year is prior to the year of the first study treatment, the month and day will be imputed as July 1st; if both day and month are missing and the year is same as the year of the first study treatment, the month and day will be imputed as January 1st. If the date is completely missing, no imputation will be performed.

Partial dates for prior anti-cancer drug therapies will be imputed as following:

- If the day is missing, it will be imputed to the first day of the month; if both day and month are missing, no imputation will be performed.

Missing or partial death dates will be imputed based on the last contact date:

- If the date is missing it will be imputed as day after date of last contact from the CRF survival page
- If the day or month is missing, death will be imputed to the maximum of the full (non-imputed) day after the date of last contact and the following:
 - Missing day: 1st day of the month and year of death
 - Missing day and month: January 1st of the year of death

If the day is missing from the date of last contact it will be imputed to 1st day of the month and year of last contact only if derived from the survival page.

No other dates will be imputed.

19 **References**

1. Eisenhauer EA. New response evaluation criteria in solid tumours: Revised RECIST guideline (version 1.1). *Eur J Cancer* 2009;45:228-47.
2. Wolchok et al. Guidelines for the evaluation of immune therapy activity in solid tumors: immune-related response criteria. *Clin Cancer Res* 2009;15(23):7412-20.

20

Appendices

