Criterion3: Histologically or cytologically proven metastatic or locally advanced solid tumor or related prior anti-cancer therapy.	Eligibility and Entry Criteria	Subject did not meet inclusion criterion 3 (histologically or cytologically proven metastatic or locally advanced solid tumor or prior anti-cancer therapy for metastatic or locally advanced disease).	PDEV03	Section 5.3.1	XX.XXDTC where XXTESTCD='TBP ALL'; SUPPXX.QNAM(F RESHDTC, FRESHTB), QVAL; CM.CMTRT, CMINDC	
Medical review required or programming.
 
List if subject did not meet all of the following requirements (depending on cohort):
 
A. Tumor tissue is available - 1) there is at least one record in XX (XX.XXDTC ne missing where XXTESTCD='TBPALL' and XXCAT='TUMOR BIOPSY OR BLOCK') for all cohorts or at least one record (missing < XX.XXDTC < TRTSDT where XXTESTCD='TBPALL' and XXCAT='UNSCHEDULED TUMOR BIOPSY OR BLOCK') for expansion subjects ; or 2) there is at least one records in SUPPXX (SUPPXX.QVAL='Y' where QNAM= 'FRESHTB') for all cohorts;
 
B. At least one prior anti-cancer therapy for NSCLC and ACC subjects - 1) there is at least one record in CM where CMCAT='PRIOR ANTI-CANCER TREATMENT' and CMSCAT='DRUG THERAPY' and CMTRT ne missing and CMINDC=('METASTATIC', 'LOCALLY ADVANCED', 'PALLIATIVE') for subjects where ACTARMCD=(MSB_EXP_NSCLC, MSB_EXP_ACC);
 
C. No prior anti-cancer therapy for first line NSCLC subjects: - 1) there is NO record in CM where CMCAT='PRIOR ANTI-CANCER TREATMENT' and CMSCAT='DRUG THERAPY' and CMTRT ne missing and CMINDC= ('METASTATIC', 'LOCALLY ADVANCED', 'PALLIATIVE') for subjects where ACTARMCD=(MSB_EXP_FLNSCLC).

	Category of Protocol Deviation	Description of Protocol Deviation	Deviation Code	Protocol Section	Variable [dataset]	Proposed check / comment

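### The PD-L1 sample-timing variable has no level for subjects without prior metastatic or locally advanced therapy, so its catch-all reports them as sampled 'after' it

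*SAP*

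**What the plan says.** Expansion SAP 13.4 plans a summary of when the tissue used for PD-L1 testing was taken. One of its two variables places the sample relative to the subject's first therapy for metastatic or locally advanced disease. It has two levels:

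- 'before', under this condition: "If the sampling date is prior to the first date of prior anti-cancer therapy for metastatic or locally advanced disease, it is considered as" such;
- 'after', as the catch-all for every remaining record: "otherwise, it is considered as" that.

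The population is not restricted to subjects who had such therapy: "All subjects with valid PD-L1 expression results will be included for the analysis".

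Other text that bears on the rule:

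- Protocol 5.3.1, first-line NSCLC: "Subjects must not have received treatment for their metastatic or recurrent disease".
- Expansion SAP Appendix I, in the programmed check for inclusion criterion 3: "No prior anti-cancer therapy for first line NSCLC subjects". The check looks for drug therapy with metastatic, locally advanced or palliative intent, the same intents that Section 14.1 counts as therapy for metastatic or locally advanced disease.
- Expansion SAP 18.2, for prior anti-cancer drug therapies: "If the day is missing, it will be imputed to the first day of the month; if both day and month are missing", nothing is imputed. Sampling dates are not on the list of dates that may be imputed.
- Expansion SAP 16.2.6: the table of objective response against PD-L1 status is "stratified by PD-L1 sampling time related to the first date of prior anti-cancer therapy for metastatic or locally advanced disease (before, after"), for the post-platinum doublet NSCLC cohort only.
- Expansion SAP 11: for qualitative variables, missing observations form their own category unless another rule is stated.

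**The concern.** A subject who never had therapy for metastatic or locally advanced disease has no date against which the sample can be earlier, so the 'before' condition fails and the catch-all assigns 'after'. The table would then say that tissue from a first-line cohort was taken after a treatment that the eligibility criteria rule out.

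The catch-all can also absorb records whose order is simply unknown. In the post-platinum NSCLC table the timing variable forms the strata. If samples that were really taken before therapy sit in the 'after' stratum, and date incompleteness is unrelated to response, any contrast between the strata is diluted. The association between PD-L1 expression and response is a stated secondary objective, so the variable should mean what its labels say.

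**Working it through.** **1. Applying the rule as written.** Code 'before' if the sampling date is earlier than the therapy date, and 'after' in every other case. Compare this with a rule that has two extra levels. The dates are illustrative.

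| Record | 13.4 read literally | With the added levels |
|---|---|---|
| Sample 1 Apr 2013, therapy start 1 May 2013 | before | before |
| Sample and therapy start on the same full date | after | after |
| Sample 1 May 2014, no metastatic or locally advanced therapy | after | not applicable |
| Sample 1 May 2013, therapy date known to the year 2013 only | after | unknown order |
| Sampling date missing, therapy start 1 May 2013 | after | unknown order |
| Sample 10 May 2013, therapy May 2013 with day missing (set to 1 May) | after | unknown order |

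Records with two full dates do not change.

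**2. Direction of the first-of-month imputation.** Let the sample fall on day *s* and the true start on day *d* of the same month. The therapy date is set to day 1. If *s* < *d*, the sample truly came first, but *s* ≥ 1, so the rule returns 'after'. If *s* ≥ *d*, the rule returns 'after' both with the true day and with day 1. The imputation can therefore move records only from 'before' to 'after', and only when both dates share a calendar month.

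**3. How many subjects have no such therapy.**

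- Planned expansion total from the cohort sizes in Protocol 5.1.5: 4×150 + 120 + 4×50 + 2×20 + 80 + 600 = 1640, which agrees with Protocol 8.1.
- First-line NSCLC is one of the "4 primary cohorts (N=150 subjects each) of" Protocol 5.1.1: 150/1640 = 9.1%.
- First-line RCC, 60 subjects, is exempt from the prior-regimen requirement in Protocol 5.3.1 but not barred from having had one. Counting all of them: (150 + 60)/1640 = 12.8%.
- Only subjects with valid PD-L1 results enter the table. The documents give an evaluable share for urothelial carcinoma only (85%, Protocol 8.1). Assuming a share between 85% and 100% here, first-line NSCLC contributes 0.85×150 = 127.5, about 128, to 150 subjects; with all first-line RCC, 0.85×210 = 178.5, about 179, to 210.
- Some platinum-ineligible urothelial and HNSCC subjects may also have had no such therapy. The documents give no number.

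**4. Which of these reach the response table.** Section 16.2.6 confines it to post-platinum NSCLC. Protocol 5.3.1 requires a platinum line in the metastatic setting there, and Appendix I flags a subject with no such record as an important deviation. Apart from deviations, only partial or missing dates can matter in that table.

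**The case against.** The best defence concerns dates. Section 11 already gives missing observations a separate category, and 13.4 does not mention missing dates, so its catch-all may be meant to sort pairs of known dates only. This stands as a fair reading. But Section 11 yields where another rule is stated, and 13.4 states one, so the SAP is ambiguous on unusable dates. The defence does not reach subjects with no prior therapy: nothing is missing for them. Section 14.1 shows the difference, since it gives the number of metastatic or locally advanced lines both a missing level and a zero level. That tabulation also lets a careful reader see that a first-line cohort had no such lines, which softens the effect without correcting the timing row.

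It can also be said that the first-of-month convention is prespecified and affects only same-month pairs. That is true, and it keeps this part small.

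Three stronger readings are tempting:

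- *First-line subjects are coded the reverse of the truth.* A reader might infer that their samples are all untreated tissue and belong under 'before'. The eligibility text bars treatment for metastatic or recurrent disease only, and Section 14.1 lists adjuvant and neo-adjuvant therapy as separate intents, so earlier exposure is possible. Neither label is true of them; the variable does not apply.
- *About 13% of the expansion phase is misclassified.* The 210 is an upper planning count, for the reasons given under first-line RCC and valid PD-L1 results. The SAP also allows reporting by cohort, where a share of the whole expansion phase is not the relevant measure.
- *The PD-L1 and response association is distorted.* First-line cohorts do not enter the stratified table, and no document shows how many post-platinum NSCLC subjects have partial dates. Dilution there is possible, not shown.

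**Conclusion.** The concern holds as a minor drafting fault. By a stated rule, compliant first-line NSCLC subjects with valid PD-L1 results would be tabulated as sampled after therapy they did not have. The planned number is 150, or about 128 if 85% are evaluable, which is an assumption carried over from urothelial carcinoma. First-line RCC and some platinum-ineligible urothelial and HNSCC subjects may add to this.

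The treatment of unusable dates is unclear rather than demonstrably wrong. The first-of-month setting can shift same-month samples in one direction only. In the stratified post-platinum NSCLC table the effect is limited to partial or missing dates and cannot be sized from the documents.

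All outputs that use the variable are descriptive or exploratory. The primary endpoint, its tests and the PD-L1 positive FAS do not depend on it.

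**What to change.** In expansion SAP 13.4, give the timing variable four levels:

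1. before;
2. after;
3. not applicable (no prior therapy for metastatic or locally advanced disease);
4. unknown order (either date unusable, or both dates in the same month with a day missing).

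In 16.2.6, leave 'unknown order' out of the stratified table and state how many subjects that removes. The first-of-month rule in 18.2 can stay for its other uses.

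The cost is a sentence in the SAP and a small programming change. The downside is slightly fewer subjects in one exploratory table.
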